3 OBJECTIVES

3.1 3.1 Study objectives

The purpose of this study is to evaluate the feasibility and preliminary effectiveness of BIPAS Alcohol, an intervention aiming to reduce pro-sipping beliefs, to encourage creation of clear, alcohol-specific rules, and to limit their provision of sips of alcohol to young adolescents.

3.2 3.2 Study outcome measures

Our primary outcome measure is changes in parents' self-reporting pro-sipping beliefs, attitudes, and practices at the end of the intervention period.

3.2.1 3.2.1 Primary outcome measures

For each participating parent, we will assess the change in composite score on an 8-item scale of self-reported pro-sipping beliefs, attitudes, and practices from baseline to 6 months (length of intervention). A four-point scale ranging from "strongly disagree" to "strongly agree" will be used, with higher values on the scale indicating a more pro-sipping belief system.

3.2.2 3.2.2 Other measures

No *a priori* secondary outcome measures.

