4 STUDY DESIGN

This study will evaluate the BIPAS Alcohol intervention with approximately 100 families. Parents will be randomized after enrollment into two groups: an intervention group and a waitlist-control group. Parents in the intervention group will begin receiving the intervention after enrollment, while parents in the waitlist-control group will receive the intervention three months after enrollment.

During the intervention period, all parents will receive text messages 2-3 times/week and online resources for three months about alcohol use and negative consequences in children, focusing on ways that they can create rules within the family environment to prevent alcohol use in children.

Parents in both groups will complete monthly surveys, and their child will complete one survey after three months. The parents in the intervention group will also receive a follow-up survey at 6 months. Parents in both groups will be asked if they would like to participate in an optional, follow-up qualitative interview about their experiences participating in the intervention.

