5.4 Treatment assignment procedures

5.4.1 Randomization procedures

We will use a coin flip to determine which group parents will randomly be assigned to after enrollment.

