6 STUDY INTERVENTION

6.1 Study intervention description

The BIPAS Alcohol intervention offers education and tools to parents of children ages 10-12 about preventing early onset alcohol use through information delivered via text message. Parents will receive text messages on early onset alcohol use, negative effects, and evidence-based recommendations about encouraging discussion and rules with their child about alcohol. Text messages will be delivered 2-3 times/week for three months.

Parents will complete a baseline survey as well as monthly surveys about alcohol-related beliefs, knowledge, and behaviors. Parents in the intervention group will also complete a follow-up survey six months after enrollment.

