7 STUDY SCHEDULE

7.1 Screening

Parents who are interested in participating will complete an online pre-screening questionnaire. Eligible families will be contacted by a member of the study team and confirm eligibility over the phone. Screening of interested families will be conducted prior to informed consent. After enrollment, study participants will be given a baseline survey and provided with additional study instructions. Successful completion of the baseline questionnaire will demonstrate a willingness and ability to participate.

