8.4 Final analyses plan

We will use generalized linear mixed models to model change in parent attitudes and behaviors over time as a function of treatment arm and baseline characteristics. We will handle missing data on survey outcomes using multilevel multiple imputation. Parameter estimates generated from these secondary analyses will be used for refining the intervention and for power analyses in a subsequent grant proposal.

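### Section 8.4 does not say how the baseline 8-item score enters the model, and one natural reading gives a less precise arm contrast than the collected data allow

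*Combined protocol and SAP*

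**What the plan says.** Section 3.2.1 defines the primary outcome as a within-parent difference: "we will assess the change in composite score on an 8-item scale of self-reported pro-sipping beliefs, attitudes, and practices from baseline to 6 months". The protocol summary gives the same 6-month time point.

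The analysis is set out in one modelling sentence in section 8.4. Generalized linear mixed models are to describe how parents' attitudes and behaviours change, "as a function of treatment arm and baseline characteristics". Multilevel multiple imputation is to handle missing survey outcomes. The section does not list the baseline characteristics, does not mention the baseline 8-item score, and does not say whether baseline is a covariate or the first of the repeated outcomes.

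The score will be available. Section 6.1 states: "Parents will complete a baseline survey as well as monthly surveys about alcohol-related beliefs, knowledge, and behaviors".

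On timing, section 4 starts the waitlist group on the intervention three months after enrollment, and sections 4 and 6.1 describe the 6-month survey for the intervention group only. Section 5.4.1 has parents "randomly be assigned to after enrollment". Section 7.1 says: "After enrollment, study participants will be given a baseline survey". Neither section says which of the two comes first.

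**The concern.** How the baseline score is handled determines the estimator, not just the length of a covariate list. A score modelled as the first repeated outcome is not also a covariate. With a free mean per arm at every time, the arm-by-time contrast is simply the difference in mean change. Demographic covariates would not in general recover the precision lost by that choice.

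Both approaches are unbiased under randomisation. They differ in how they treat chance imbalance, which is plausible here because allocation is by coin flip and no stratification on the baseline score is described. A change score subtracts the whole baseline difference between arms, whereas only a fraction rho of it is expected to persist at follow-up (with equal SDs), so it over-corrects.

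What is at stake is the width of the interval. Section 8.2 concedes low power for small differences and gives effect-size estimation for a larger trial as one purpose. Section 8.4 sends the parameter estimates to a later power analysis. An avoidably wide interval weakens one of the pilot's main products.

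**Working it through.** **Inputs.** From the documents: about 100 families (section 4) and a coin flip (section 5.4.1), taken as 50 per arm. The documents give no alpha, SD, effect size, baseline-to-follow-up correlation (rho) or dropout rate, so there is no planned figure to reproduce. Assumed: SD = 1 at each time, complete data, two-sided alpha 0.05, rho from 0.3 to 0.8.

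**Variance per parent.**
- Change score: Var(Y3 - Y0) = 1 + 1 - 2·rho = 2(1-rho).
- Adjusted for baseline: 1 - rho^2.
- Ratio, adjusted to change: (1-rho)(1+rho) / [2(1-rho)] = (1+rho)/2, which is below 1 for every rho below 1.

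**Variance of the arm contrast.** Multiply by 2/50 = 0.04. The 95% half-width is 1.96 times the square root. The interval narrows by 1 - sqrt((1+rho)/2).

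| rho | Change: variance | Adjusted: variance | Ratio | Half-width, change vs adjusted (SD) | Narrower by |
|---|---|---|---|---|---|
| 0.3 | 0.04 × 1.40 = 0.0560 | 0.04 × 0.91 = 0.0364 | 0.65 | 0.46 vs 0.37 | 19% |
| 0.5 | 0.04 × 1.00 = 0.0400 | 0.04 × 0.75 = 0.0300 | 0.75 | 0.39 vs 0.34 | 13% |
| 0.7 | 0.04 × 0.60 = 0.0240 | 0.04 × 0.51 = 0.0204 | 0.85 | 0.30 vs 0.28 | 8% |
| 0.8 | 0.04 × 0.40 = 0.0160 | 0.04 × 0.36 = 0.0144 | 0.90 | 0.25 vs 0.24 | 5% |

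In families, 100 divided by the ratio gives an equivalent of about 154, 133, 118 and 111.

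**Check in a mixed model.** Exact generalised least squares variances were computed for four waves (months 0 to 3), compound symmetry and 50 per arm, at rho 0.3, 0.5 and 0.7. With free arm-by-time means, the month-3 change contrast has variance 0.056, 0.040 and 0.024. With the arms constrained to a common baseline mean, it has 0.0364, 0.0300 and 0.0204. These match the table, so a mixed model does not by itself recover the gain; the treatment of baseline does.

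**Power (normal approximation, change vs adjusted).**

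| Effect | rho 0.3 | rho 0.5 | rho 0.7 | rho 0.8 |
|---|---|---|---|---|
| 0.2 SD | 13% vs 18% | 17% vs 21% | 25% vs 29% | 35% vs 39% |
| 0.5 SD | 56% vs 75% | 71% vs 82% | 90% vs 94% | 98% vs 99% |

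For small effects the trial stays underpowered either way. Adjustment costs about one degree of freedom.

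**Where the gain applies.** Up to month 3 the waitlist arm is untreated. After that both arms have received or are receiving the intervention, and the extra 6-month survey is described for one arm only. Neither variance formula therefore describes a randomised comparison at 6 months.

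**The case against.** The strongest reply is that the plan states no inferior method. The baseline 8-item score can naturally be one of the baseline characteristics, and nothing in the documents excludes it. Defining the outcome as change does not settle the matter either, since a change outcome regressed on arm and baseline score gives the adjusted arm estimate. This stands. A reader might infer from section 8.4 that the plan has chosen the unadjusted change-score analysis and so certainly forfeits precision. The text does not support that, because the loss arises under one permitted reading and vanishes under another. What the reply leaves untouched is that the choice is not made, and the sentence is easily implemented the less efficient way.

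Second, the size is unknown. Every figure rests on an assumed correlation, and the power gain looks large only for a medium effect and low rho. This also stands; interval width is the fairer measure for a pilot.

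Third, section 8.4 itself calls these analyses secondary and the study is a feasibility trial. That limits the weight of the point, but the same section relies on the estimates for a later power calculation.

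Fourth, section 6.2 mentions monthly surveys for up to six months, so waitlist parents might also be surveyed at month 6. Even so, they would by then have been offered the intervention, and no untreated concurrent comparison would exist.

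On ordering, a reader might infer that parents learn their arm before completing the baseline survey. The documents do not say so. Section 7.1 treats completing the baseline questionnaire as evidence of willingness to participate, which is compatible with baseline coming first. The order is open, not shown to be wrong.

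**Conclusion.** The point holds as under-specification with a possible, avoidable loss of precision. If baseline is fitted as the first repeated outcome with a free mean in each arm, the month-3 arm contrast has a variance that adjustment would cut by 35%, 25%, 15% or 10% at rho 0.3, 0.5, 0.7 or 0.8. The figures assume equal SDs and complete data; the absolute half-widths also assume 50 per arm. If the analysts already intend to adjust for the baseline score, nothing is lost and the text only needs to say so.

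The gain is confined to the contrast up to month 3. Adjustment cannot supply the missing concurrent control for the 6-month primary outcome in the summary and section 3.2.1, and that conflict with sections 4 and 6.1 has to be resolved in its own right. The order of survey and assignment is a secondary clarification. It matters because there is no masking (section 5.4.2) and a self-reported attitude score collected after the arm is known could be affected by it.

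**What to change.** 1. In section 8.4, state that post-baseline composite scores are modelled on arm, time and arm-by-time with the baseline 8-item score as a covariate; alternatively, keep baseline among the outcomes and constrain the arms to a common baseline mean. List any other baseline characteristics.
2. Use the same specification in the multilevel imputation model, including the baseline score and the arm-by-time terms.
3. Report the randomised arm difference with its 95% confidence interval.
4. Reconcile the 6-month primary outcome in the summary and section 3.2.1 with the schedule in sections 4 and 6.1: make the month-3 arm difference the randomised estimate, and report the 6-month change as within-arm. This changes the stated primary time point, so it needs an explicit amendment with a reason, not just a line in 8.4.
5. In sections 5.4.1 and 7.1, state that the baseline survey is completed before the arm is assigned and revealed.

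Items 1 to 3 and 5 take a few sentences. Item 4 also touches the summary and section 3.2.1. No additional data collection is required, and the analytic cost is about one degree of freedom.

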9 ETHICS/PROTECTION OF HUMAN SUBJECTS

9.1 Ethical standard

The investigator will ensure that this study is conducted in full conformity with the principles set forth in The Belmont Report: Ethical Principles and Guidelines for the Protection of Human Subjects of Research, as drafted by the US National Commission for the Protection of Human Subjects of Biomedical and Behavioral Research (April 18, 1979) and codified in 45 CFR Part 46 and/or the ICH E6; 62 Federal Regulations 25691 (1997).

9.2 Institutional Review Board

Study procedures have been approved by the University of North Carolina Institutional Review Board.

9.3 Informed consent process

Informed consent will be obtained from all participating families prior to participation in baseline data collection.

9.4 Exclusion of women, minorities, and children (special populations)

Not applicable.

9.5 Subject confidentiality

Participant confidentiality and privacy is strictly held in trust by the participating investigators, their staff, and the sponsor(s) and their agents. The study team will take precautions to ensure that subject confidentiality is maintained. All data will be stripped of patient-level identifiers and stored on a password-protected server accessible only to UNC study staff. Data will be reported in aggregate and will not identify participating parents or children by name.

9.6 Study discontinuation

Not applicable.

9.7 Future use of stored specimens

Not applicable.
